If feasible based on guidelines/recommendations related to the COVID-19 pandemic (e.g., physical distancing), the study will also be conducted at the clinical trial unit (CTU), Dhaka. The study area includes the adjoining slum and non-slum areas of icddr,b Mohakahli, Dhaka - Kunipra, Arjat Para, Nakhalpara, Korail, Begunbari, Chairman bari and Badda. Participants will attend CTU, which is about one kilometer from the areas. The population is approximately 300,000 and literacy is ~50%. It is stable with low socio-economic conditions. The population is mainly engaged in industrial labour, garment factory, small businesses and rickshaw pullers.

Study staff will identify infants eligible to be vaccine recipients through house-to-house visits at the two proposed sites of Mirpur and Mohakahli.

Study Design

This is an open-label, non-inferiority, balanced three arm randomized clinical trial assessing immunogenicity of poliovirus vaccines. Vaccine recipients will be identified through active surveillance of new births in the community and parents will be requested to participate through home visits by local field workers. Vaccine recipients will be enrolled at 6 weeks of age, randomly assigned to one of the three arms and followed to 18 weeks of age.

Inclusion Criteria

Criteria for both vaccine recipient and sibling must be met for enrolment in the trial.

Vaccine Recipient

1. Healthy infants 6 weeks of age (range: 42–48 days).
2. Parents that consent for participation in the full length of the study.
3. Parents that can understand and comply with planned study procedures.
4. Infant has at least one sibling aged <10 years living in the same household that is eligible for participation in the study and can be enrolled at the same time as the vaccine recipient.

Sibling

1. Healthy child aged <10 years.
2. Sibling of the vaccine recipient and resides in the same household.
3. Parents that consent for participation in the study until and including the Clinic Visit at 10 weeks (age of vaccine recipient).
4. Parents that can understand and comply with planned study procedures

Exclusion Criteria

If either vaccine recipient or sibling meets the exclusion criteria, then neither can be enrolled in the trial.

Vaccine Recipient

1. Parents, infants, and siblings who are unable to participate in the full length of the study (e.g., plan to move away from the study area during the study period).

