2. A diagnosis or suspicion of immunodeficiency disorder either in the infant or in an immediate family member.
3. A diagnosis or suspicion of bleeding disorder that would contraindicate administration of bOPV or nOPV2 or collection of blood by venipuncture.
4. Acute diarrhoea, infection or illness at the time of enrolment (6 weeks of age) that would require infant's admission to a hospital.
5. Acute vomiting and intolerance to liquids within 24 hours before the enrolment visit (6 weeks of age).
6. Evidence of a chronic medical condition identified by a study medical officer during physical exam.
7. Receipt of any polio vaccine (OPV or IPV) before enrolment based upon documentation or parental recall.
8. Known allergy/sensitivity or reaction to polio vaccine, or its contents.
9. Infants from multiple births. Infants from multiple births will be excluded because the infant(s) who is/are not enrolled would likely receive OPV through routine immunization and transmit vaccine poliovirus to the enrolled infant. Even if all births from a multiple birth could be enrolled in the study, we will exclude multiple births as discontinuation of one may lead to discontinuation of multiple vaccine recipients.
10. Infants from premature births (<37 weeks of gestation).

Sibling

1. Participant in a previous poliovirus vaccine clinical trial.
2. Unable to participate in the study until and including the Clinic Visit at 10 weeks (age of vaccine recipient).
3. A diagnosis or suspicion of immunodeficiency disorder either in the sibling or in an immediate family member.
4. Acute diarrhoea, infection or illness at the time of enrolment that would require sibling's admission to a hospital.
5. Evidence of a chronic medical condition identified by a study medical officer during physical exam.

Discontinuation Criteria

Vaccine Recipient

1. Withdrawal of consent for participation for any reason.
2. Request by parents of vaccine recipient to terminate all study procedures.
3. Identification of immunodeficiency disorder, bleeding disorder or another medical condition for which continued participation, in the opinion of the principal investigator, would pose a risk to the vaccine recipient to continue in the study.
4. Receipt of immunosuppressive medications.

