Clinic Visit at 6 weeks of Age – Vaccine RecipientDate of visit (dd/MMM/yy): / / Date of birth (dd/MMM/yy): / / Sex: F / M**Demographics**

Father's education (circle): No formal school / Primary / Middle / High school / Graduate

Mother's education (circle): No formal school / Primary / Middle / High school / Graduate

Eligibility criteria for vaccine recipient

1. Child's residence within the study area? Yes / No
2. Child 6 weeks of age? Yes / No
3. Child and family NOT planning to travel / move in the next 3 months that would prevent them from coming for study follow-up visits? Yes / No
4. Child born in single birth? Yes / No
5. Child born after 37 weeks of pregnancy? Yes / No
6. No diagnosis or suspicion of immunodeficiency in the child or family member? Yes / No
7. Child has NO known coagulation disorders that contraindicates venipuncture or injection? Yes / No
8. Child has NOT received OPV or IPV before? Yes / No
9. Child does not have a medical condition that contraindicates bOPV or nOPV2 administration? Yes / No

If no, specify _____

10. Child has at least one sibling < 10 years living in the household? Yes / No

Is this child eligible for participation in the study as a vaccine recipient? Yes / No

- *Child is ELIGIBLE if all answers to questions 1-10 are YES. If the child is eligible, proceed to the next section.*
- *Child is NOT ELIGIBLE if any of the answers to questions 1-10 is NO. If the child is NOT eligible, STOP.*

Do the parents give consent for their child to participate in the study as a vaccine recipient? Yes / No

- *If parents DO NOT consent, ask them the following. When finished, thank them for their time and STOP.*

Why are you not interested in having your child participate in the study? (Circle all that apply) Study purpose unclear / Vaccine concerns / Reluctant to blood draw / More than two vaccine injections at first visit / Busy-No time / Other (specify): _____

- *If parents DO consent, continue with the study procedures.*

Clinic Visit at 6 weeks of Age – Vaccine Recipient

1. Is the child currently breastfed? No breastfeeding / Partial breastfeeding / Exclusive breastfeeding
2. Has the child received BCG? Yes / No
- 2a. If yes, date of vaccination (dd/MMM/yy): / /
3. Has the child received any other vaccine to date? Yes / No
- 3a. If yes, specify: _____
- 3b. Date of vaccination (dd/MMM/yy) / /
4. Has any other child in the household received OPV since the infant was born? Yes / No
- 4a. If yes, specify: _____

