2b. Date of vaccination (dd/mm/yy): / /
3. Has any other child in the household received OPV since the last clinic visit ? Yes / No 3a. If yes, specify: _____
4. Has the child had diarrhea in the last 24 hours (≥ 3 loose stools in 24 hours)? Yes / No
4a. If yes, specify: duration of diarrhea in days:
(If the child currently has fever $>38.3^{\circ}\text{C}$, blood in stools, vomiting or signs of dehydration, do not continue with study procedures. Provide advice and referral as required.)
5. Has the child been sick since the last study visit? Yes / No 5a. If yes, specify: _____
6. Is the child on any immunosuppressive medications? Yes / No 6a. If yes, specify _____

Physical Exam

7. Temperature: . $^{\circ}\text{Celsius}$
8. Length #1: . cm
9. Length #2: . cm
10. Weight #1: . kg
11. Weight #2: . kg

Blood Collection

12. Blood sample collected? Yes / No 12a. If not, why? _____
13. Sufficient quantity (1 ml)? Yes / No 13a. If insufficient, why? _____
14. Time of collection (hh:mm): :

Vaccine Administration*If Study Arm A or B*

15. nOPV2 administered? Yes / No 15a. If not, reason: _____
If administered: 15b. Time of vaccine administration (hh:mm): :
15c. Expiration (mmm/yy): /

If Study Arm B or C

16. bOPV administered? Yes / No 16a. If not, reason: _____
If administered: 16b. Time of vaccine administration (hh:mm): :
16c. Expiration (mmm/yy): /

Clinic Visit at 10 weeks of Age (ctd.)

17. Pentavalent administered? Yes / No 17a. If not, reason: _____

If administered: 17b. Dose: Penta1 / Penta2 / Penta3

17c. Site of administration: Right thigh / Left thigh

18. PCV administered? Yes / No 18a. If not, reason: _____

If administered: 18b. Dose: PCV1 / PCV2 / PCV3

18c. Site of administration: Right thigh / Left thigh

Observe for 30 minutes after vaccine administration:

19. Any symptoms? Yes / No

19a. If yes, specify (*complete Adverse Event Form, if required*): _____

The following questions correspond to sibling of the study vaccine recipient. Note: the sibling does not need to be present for this visit.

20. Has the child received any poliovirus vaccines (bOPV, fIPV) since last visit? Yes / No

20a. If yes, specify: / /

20b. Date of vaccination (dd/mm/yy): _____

21. Has the child had diarrhea in the last 24 hours (≥ 3 loose stools in 24 hours)? Yes / No21a. If yes, specify: duration of diarrhea in days

22. Has the child been sick since the last study visit? Yes / No 22a. If yes, specify: _____

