23. Is the child on any immunosuppressive medications? Yes / No 23a. If yes, specify _____

Schedule next visit date (dd/mm/yy): / /

Name and signature of medical officer: _____

Clinic Visit at 14 weeks of AgeDate of visit (dd/mm/yy): / / **Clinical History**

1. Is the child currently breastfed? No breastfeeding / Partial breastfeeding / Exclusive breastfeeding
2. Has the child received any vaccine since last visit? Yes / No 2a. If yes, specify: _____
2b. Date of vaccination (dd/mm/yy): / /
3. Has any other child in the household received OPV since the last clinic visit? Yes / No 3a. If yes, specify: _____
4. Has the child had diarrhea in the last 24 hours (≥ 3 loose stools in 24 hours)? Yes / No
4a. If yes, specify: duration of diarrhea in days:
(If the child currently has fever $>38.3^{\circ}\text{C}$, blood in stools, vomiting or signs of dehydration, do not continue with study procedures. Provide advice and referral as required.)
5. Has the child been sick since the last study visit? Yes / No 5a. If yes, specify: _____
6. Is the child on any immunosuppressive medications? Yes / No 6a. If yes, specify _____

Physical Exam

7. Temperature: . $^{\circ}\text{Celsius}$
8. Length #1: . cm
9. Length #2: . cm
10. Weight #1: . kg
11. Weight #2: . kg

Blood Collection

12. Blood sample collected? Yes / No 12a. If not, why? _____
13. Sufficient quantity (1 ml)? Yes / No 13a. If insufficient, why? _____
14. Time of collection (hh:mm): :

Vaccine Administration*If Study Arm A or B*

15. nOPV2 administered? Yes / No 15a. If not, reason: _____
- If administered: 15b. Time of vaccine administration (hh:mm): :
- 15c. Expiration (mmm/yy): /

Clinic Visit at 14 weeks of Age (ctd.)

If Study Arm B or C

16. bOPV administered? Yes / No 16a. If not, reason: _____

If administered: 16b. Time of vaccine administration (hh:mm):

--	--	--	--	--

 :

--	--	--

16c. Expiration (mmm/yy):

--	--	--	--

 /

--	--

17. Pentavalent administered? Yes / No 17a. If not, reason: _____

If administered: 17b. Dose: Penta1 / Penta2 / Penta3

17c. Site of administration: Right thigh / Left thigh

18. PCV administered? Yes / No 18a. If not, reason: _____

If administered: 18b. Dose: PCV1 / PCV2 / PCV3

18c. Site of administration: Right thigh / Left thigh

Observe for 30 minutes after vaccine administration:

19. Any symptoms? Yes / No

19a. If yes, specify (*complete Adverse Event Form, if required*): _____Schedule next visit date (dd/mm/yy):

--	--	--	--

 /

--	--	--

 /

--	--

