Outcome (circle what applies): Ongoing / Resolved without sequela / Resolved with sequela / DeathDate when event resolved or death (dd/mm/yy): / /

Did this AE lead to discontinuation from the study or from future vaccinations? Yes / No

Adverse Event Form (cont.)**Study group allocation:** Specify which study group the child was allocated (*circle the answer*):

A: nOPV2 @ 6, 10, and 14 weeks
 B: nOPV2 + bOPV @ 6, 10, and 14 weeks
 C: bOPV @ 6, 10, and 14 weeks

Study vaccines administered:

Clinic visit	Study vaccines administered	Date (DD/MMM/YY)	Lot & batch number
6 weeks of age		____ / ____ / ____	
10 weeks of age		____ / ____ / ____	
14 weeks of age		____ / ____ / ____	

Routine immunization vaccines administered:

Clinic visit	Vaccines administered
At birth	
6 weeks of age	
10 weeks of age	
14 weeks of age	
18 weeks of age	
At any other age, specify age _____	

Signature of study investigator/s: _____

To be completed by the principal investigator

Is the event related to the study vaccine?

Unrelated Possibly related Probably related Definitely related

If unrelated to the vaccine, provide a reasonable explanation for the event (*e.g., other vaccine, blood collection, medical collection, etc.*) _____

_____Name and signature of PI: _____ Date / / /

Discontinuation Tracking Form – Vaccine Recipient

Date of the report (dd/mm/yy): / /

Date of study discontinuation (dd/mm/yy): / /

Note: This is the date the vaccine recipient is withdrawn from the study and may not be the same date as the report

Last clinic visit (circle one): 6 weeks / 10 weeks / 14 weeks

Date of last study clinic visit (dd/mm/yy): / /

Reasons (circle one of the choices listed below):

Discontinuation criteria as mentioned in study protocol:

1. Parent withdrew consent for participation (i.e., did not want child to participate any further).
2. The vaccine recipient received **polio vaccine** outside of the study. (**Complete protocol deviation form**)
3. Parent refused to allow collection of blood at 6 weeks of age. (**Complete protocol deviation form**)
4. Study staff were unable to collect blood at 6 weeks of age (**Complete protocol deviation form**)
5. Since enrolment, the vaccine recipient was diagnosed with a medical condition in which continued participation in the study posed a health risk (for example, immunodeficiency or bleeding disorder).
6. The vaccine recipient began taking immunosuppressive medications.

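### Immunodeficiency in the family bars enrolment, but after dose 1 the stopping rule weighs only the infant's own risk and the family question is not asked again before doses 2 and 3

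*Protocol*

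**What the plan says.** **At entry.** In the Protocol, Exclusion Criteria, vaccine recipient item 2 excludes for "A diagnosis or suspicion of immunodeficiency disorder either in the infant or in an immediate family member". Sibling item 3 is parallel: "A diagnosis or suspicion of immunodeficiency disorder either in the sibling or in an immediate family member". The opening rule of that section ties the pair together: "If either vaccine recipient or sibling meets the exclusion criteria, then neither can be enrolled in the trial". On the 6-week vaccine recipient form (Appendix A), eligibility item 6 puts this to the parents: "No diagnosis or suspicion of immunodeficiency in the child or family member".

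**After dose 1.** Under Discontinuation Criteria, vaccine recipient item 3 names immunodeficiency among conditions that can end participation. It applies only where, in the principal investigator's opinion, the condition "would pose a risk to the vaccine recipient to continue in the study". The three sibling criteria are discontinuation of the recipient, withdrawal of consent, and receipt of polio vaccine.

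**At the later dose visits.** The 10-week form has two sibling items close to the subject: "Has the child been sick since the last study visit? Yes / No 22a. If yes, specify" (item 22) and "Is the child on any immunosuppressive medications? Yes / No 23a. If yes, specify" (item 23). The 14-week form has no sibling health item.

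**The concern.** The Protocol treats diagnosed or suspected immunodeficiency in a close relative as reason enough to refuse both children. The same information arriving between week 6 and week 14 has no rule attached and no scheduled question to bring it out. Followed literally, the plan allows one or two further live nOPV2 doses in a household that it would have turned away at the door.

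The section on risks to vaccine recipients and siblings accepts some VAPP risk in close contacts. It calls that risk minimal because routine coverage is high and nOPV2 is designed to be less prone to reversion. Neither reason deals with a contact whose immune system is deficient. What is at stake is the safety of a small number of household contacts, and consistency between the entry rule and the stopping rule.

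**Working it through.** There is no figure in the plan to reproduce. The check sets the entry rules beside the rules and forms that apply after dose 1.

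| Question | At entry (6 weeks) | Before doses 2 and 3 |
|---|---|---|
| Whose immunodeficiency counts? | Infant, sibling or immediate family member | Recipient criterion 3 does not say whose; tracking-form reason 5 words it as a diagnosis in the recipient |
| Is suspicion enough? | Yes | Criterion 3 speaks of identification; the tracking form speaks of diagnosis |
| Whose risk is weighed? | Not stated | The recipient's only (criterion 3) |
| Are parents asked about the family? | Yes, recipient form item 6 | No, on neither form |
| Is there a stop instruction? | Yes, the pair is ineligible | Only for the infant's fever, bloody stool, vomiting or dehydration (item 4 of each form) |

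**Count of criteria and forms**
- Recipient discontinuation criteria naming immunodeficiency in a sibling or relative: 0 of 9.
- Sibling discontinuation criteria naming immunodeficiency: 0 of 3.
- Forms for doses 2 and 3 that repeat the family question: 0 of 2.
- The 6-week sibling form also leaves out sibling exclusion 3, so item 6 on the recipient form is the only form item that captures it.

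**Other rules that might close the gap**
- Concomitant Medications and Vaccines discontinues a child on immunosuppressive medication, but only the vaccine recipient.
- Items 22 and 23 of the 10-week form concern one sibling's sickness and medication, not family immunodeficiency. They are printed after the vaccine and observation items, and no action follows from a yes.
- Both tracking forms offer withdrawal by the investigator with a reason to be specified. They list it under "Discontinuation criteria as mentioned in study protocol", yet it is not among the nine recipient or three sibling criteria in the Protocol body. It permits action but prompts none.

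**Scale**
- Arms A and B at the enrolment target: 265 x 2 = 530 households. At the unadjusted size: 238 x 2 = 476.
- Times the repeated question would be asked in those arms, over two visits: 530 x 2 = 1,060, or 476 x 2 = 952.
- Arm C receives bOPV at the ages of the national schedule, so a hold changes little there relative to routine care.
- The documents give no rate of newly recognised immunodeficiency in families, so no expected number of affected households is calculated.

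**The case against.** The strongest reply is that this is an omission, not a contradiction, and that the purpose of the entry bar is never stated. It refers to immediate family, which is kinship and not household contact. If the aim is to flag heritable risk to the infant, criterion 3 may already carry it forward, since it does not say whose disorder must be identified. That stands as a possible reading. It still leaves nothing scheduled after week 6 that would bring a relative's diagnosis to the investigator, and it leaves contact risk outside the criterion.

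Other routes exist: parents can withdraw, a medical officer examines the infant at each dose visit, and the investigator can withdraw a child. The 10-week procedure lists completing the eCRF before vaccination, so the sibling items may be asked in time for dose 2. The consent pages and SOPs are not available here, and they may tell parents what to report. These points lower the size of the concern. They do not supply a rule or a prompt.

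A reader might draw three stronger conclusions that the documents do not support.
- *That the projected day-14 shedding (53% in recipients, 23% in siblings under 5) measures the harm.* Those projections follow the first dose. The fix affects only doses 2 and 3, and the last study stool sample is at 10 weeks, after one dose. The Justification section chose the stool times for children without existing mucosal immunity, which if anything suggests less shedding later.
- *That a probability of an affected household can be given.* Any such figure would come wholly from an assumed incidence.
- *That the sibling's immunosuppressive medication should also stop dosing.* It is not an entry bar, and sibling participation is consented only up to the 10-week clinic visit, which also explains why sibling items end there.

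**Conclusion.** The point holds as a cheap improvement, worth considering. The entry rule protects against immunodeficiency in the infant, the sibling and close relatives. The rule after dose 1 weighs risk to the infant alone, and the question that would reveal a change is not repeated. Unprompted discretion is what remains.

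The benefit is a small, unquantified safety gain, mainly in Arms A and B, where nOPV2 exposure comes from the trial. Dose 1 has already exposed the household, so the fix can prevent only the added exposure from doses 2 and 3. Nothing changes for sample size, power or the primary comparison.

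The conclusion rests on the Protocol text and Appendix A forms alone. It assumes that no SOP or consent wording already requires parents to report a new family diagnosis and staff to hold the dose.

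**What to change.** 1. Extend recipient discontinuation criterion 3: if immunodeficiency is newly diagnosed or suspected in the infant or an immediate family member, including the sibling, the next study OPV dose is held until the principal investigator has reviewed the risk to the infant and to household contacts.
2. Repeat item 6 of the 6-week recipient form as one parent-answered question in the Clinical History section of the 10- and 14-week forms, ahead of the vaccine items, with the instruction to hold the dose and refer to the principal investigator if the answer shows a new diagnosis or suspicion. That section already has a household question (item 3) and a stop instruction (item 4). The sibling need not attend.

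**Cost.** One amended criterion and one question on each of two existing forms, with ERC and RRC approval as a protocol modification. No new visit, test or staff is needed. A held dose may fall outside the 3-day window and take the infant out of the per-protocol set. It also delays that infant's polio protection, because study OPV replaces the routine polio vaccine and fIPV is deferred to 18 weeks. The principal investigator's review should weigh that delay against the contact risk. The change governs study doses only; the bOPV doses given to Arms A and B from 18 weeks lie outside it.
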